## 12. Statistical Methods

All analyses will use SAS version 9.4 or higher.

Categorical variables will be summarized using counts and percentages based on the specified population total. Percentages will be rounded to one decimal place, except 100% will be displayed without any decimal places and percentages will not be displayed for zero counts.

Continuous data will be summarized using non-missing observations (n, mean, standard deviation (SD), median, Quartile 1, Quartile 3, minimum, and maximum). The median, minimum, and maximum values will be displayed to the same level of the precision as the raw value. Mean, median, Q1 and Q3 will be rounded to 1 decimal place greater than the precision of the original value. The SD will be rounded to 2 decimal places greater than the precision of the original value. Confidence intervals, least square mean (LSM) and standard error (SE) will be provided as appropriate. Confidence intervals, LSM will present the same precision as the mean value whereas SEs will present the same precision as SD.

P-values will be rounded to 3 decimal places. P-values less than 0.001 will be presented as “<0.001” and p-values greater than 0.999 will be presented as “>0.999.”

Statistical hypothesis testing will be one-sided and carried out at the 5% level of significance. Testing will be performed on the primary endpoint and secondary endpoints as appropriate. No adjustments for multiplicity will be made.

If there is strong collinearity between the baseline EASI score/BSA score/IGA score and the baseline severity of AD (moderate versus severe), the continuous baseline score will be included the efficacy analysis.

All the listings will be displayed by treatment arm, patient identifier and date of assessment. Age, gender, and race will be presented on each listing.

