#### 12.4.3.4. Primary Analysis

The primary efficacy analysis will be the treatment comparison between ATI-1777 and vehicle for the percent change from baseline in EASI scores at Week 4 based on the FAS. Change from baseline is calculated as described in [section 10.1.3](#). This treatment comparison will be made within the context of a Mixed Model Repeated Measures (MMRM) analysis where the EASI scores over time are treated as repeated measures within a given patient. Treatment group, time (study visit), treatment by time interaction, and baseline severity of AD will enter the model as categorical factors, baseline EASI score will be included as a continuous covariate, and patient ID will enter the model as a random effect. Treatment group model-based means and model-based differences in treatment groups will be provided along with corresponding 90% confidence intervals and p-values. If the MMRM model will not converge or if there is strong collinearity between the baseline EASI score and the baseline severity of AD, one or both of the covariates may be excluded from the primary analysis.

For the primary efficacy analysis on the FAS population, missing data will be imputed using LOCF. Missing data will not be imputed for the analyses that are based on the PP population.

The null hypothesis is that the LSM contrast between ATI-1777 and vehicle at Week 4 equals zero. Significance tests will be based on least-squares means using a one-sided test at  $\alpha = 0.05$  (one-sided p-value compared to 0.05). A symmetric two-sided 90% confidence interval will accompany the corresponding p-value. The MMRM will be fit with covariance matrices of UN (unstructured), CS (compound symmetry), TOEPH (Heterogeneous Toeplitz) and ARH(1) (Heterogeneous auto-regressive 1). The analysis with the lowest Akaike's information criterion (AIC) will be reported in the table. Other covariance matrix structures may be used if none of these converge. The Kenward-Roger approximation will be used to estimate the denominator degrees of freedom.

The estimates at the timepoint Week 4 will be considered as primary. Least squares mean, Standard Errors, for each treatment group, least squares mean difference (ATI-1777 minus vehicle), and 90% confidence intervals for the

difference between the treatment groups and the corresponding one-sided p-value will be reported. The following SAS code will be used.

```
proc mixed data= datain method=ml;
  class treatment visit baseline ADseverity;

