  model pchg_EASI = baseline_EASI baseline_ADseverity visit treatment treatment*visit
    / cl solution ddfm=kr alpha=0.10;
  repeated /type=un subject=usubjid;
  slice treatment * visit /sliceby=visit means diff nob cl;
  ods output slices = lsm sliceDiffs = diff;
run;
```

Summary statistics (n, mean, SD, minimum, Q1, median, Q3, and maximum) of the baseline value, the value at Week 4 and the corresponding change from baseline for EASI score will be presented by treatment group and overall using the FAS..

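### The prescribed SAS code fits the primary MMRM by maximum likelihood rather than REML; with 34 to 50 patients the standard errors come out about 3–5% too small and the one-sided 5% test runs at about 5.4–6%.

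*SAP*

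**What the plan says.** SAP section 12 sets the error rate: "Statistical hypothesis testing will be one-sided and carried out at the 5% level of significance". Section 12.4.3.4 adds that "A symmetric two-sided 90% confidence interval will accompany the corresponding p-value" and that "The Kenward-Roger approximation will be used to estimate the denominator degrees of freedom". Four covariance structures (unstructured, compound symmetry, heterogeneous Toeplitz, heterogeneous AR(1)) are to be fitted, and the one with the lowest AIC reported.

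The text does not name an estimation method. Only the code does. It is introduced by "The following SAS code will be used" and begins "proc mixed data= datain method=ml". The rest specifies "model pchg_EASI = baseline_EASI baseline_ADseverity visit treatment treatment*visit" with the options "cl solution ddfm=kr alpha=0.10", followed by "repeated /type=un subject=usubjid". By contrast, the logistic code for EASI-50 in section 12.4.4.1 is labelled an example.

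The protocol (section 9.4.5) asks for an MMRM and says nothing about how it is estimated.

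**The concern.** ML estimates the residual covariance as if the mean were known. The primary model has eight mean parameters over three post-baseline visits (Days 8, 15 and 28): three visit means, three treatment-by-visit effects, baseline EASI and baseline severity. With a few dozen patients that omission is not negligible, and variances come out too small. REML exists to correct it. Kenward-Roger was built on REML estimates. It sets the degrees of freedom and adjusts for uncertainty in the estimated covariance, but it does not replace the ML divisor.

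If so, the primary p-value and interval are too favourable to ATI-1777, and the stated 5% and 90% are not what the code delivers. EASI at the earlier visits comes from the same fit. Change in IGA, BSA and PP-NRS is to use a similar model, with no multiplicity adjustment.

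A second, smaller matter is that the REPEATED statement names no visit effect, so SAS matches a patient's records to covariance positions by order. In the per-protocol analysis, where missing values are not imputed, a patient with no Day 8 record would have Day 15 and Day 28 treated as the first and second visits.

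**Working it through.** **Inputs from the documents.** Three post-baseline visits and the fixed effects above (SAP section 12.4.3.4); 1:1 allocation; one-sided alpha 0.05; 34 completers (both documents); 50 enrolled (protocol section 9.3) or 42 enrolled (SAP section 8.3); means of 65% and 20%; spread 38.3. The FAS is filled by LOCF, so complete vectors were simulated.

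**Inputs assumed.** Visit correlations of 0.5, 0.65 or 0.8 for the unstructured (UN) runs and 0.6 for compound symmetry (CS); 25% of patients severe; visit SDs 30/35/38.3 for UN and 38.3 throughout for CS.

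**The plan's own figure.** With 17 per arm, difference 45 and 38.3 read as an SD, the noncentrality is 45 / (38.3 × √(2/17)) = 3.43. With 32 df and one-sided 0.05, power is 95.6%, as stated. The figure 38.3, which the documents call a variance, reproduces this only as an SD.

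**Analytic size of the bias.** If p mean parameters effectively bear on the Week 4 contrast, the ML/REML standard-error ratio is r = √((n − p)/n), and the true one-sided error is P(T > r × t₀.₉₅) on n − p df. With p = 3:

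- n = 34: r = √(31/34) = 0.955, shortfall 4.5%, error 5.8%
- n = 42: r = √(39/42) = 0.964, shortfall 3.6%, error 5.6%
- n = 50: r = √(47/50) = 0.969, shortfall 3.1%, error 5.5%

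With p = 4 the shortfalls are 6.1%, 4.9% and 4.1%, and the errors 6.1%, 5.9% and 5.7%.

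**Simulation under the null.** Each trial was fitted by ML and by REML, with Kenward-Roger standard errors and df computed from each fit. There were 4,000 trials per setting (8,000 at correlation 0.65), giving a Monte Carlo SE of about 0.2 points on the error rate.

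| N | Structure, correlation | SE shortfall of ML | One-sided error ML / REML | 90% CI coverage ML / REML |
|---|---|---|---|---|
| 34 | UN, 0.5 | 4.6% | 6.0% / 5.2% | 88.0% / 89.7% |
| 34 | UN, 0.65 | 4.7% | 5.9% / 4.9% | 88.1% / 90.1% |
| 34 | UN, 0.8 | 4.8% | 5.8% / 5.0% | 88.3% / 90.0% |
| 42 | UN, 0.5 | 3.7% | 5.7% / 4.9% | 88.7% / 90.2% |
| 42 | UN, 0.8 | 3.9% | 5.8% / 4.9% | 88.5% / 90.2% |
| 50 | UN, 0.5 | 3.1% | 5.4% / 4.8% | 89.3% / 90.4% |
| 50 | UN, 0.65 | 3.2% | 5.4% / 4.9% | 89.2% / 90.3% |
| 50 | UN, 0.8 | 3.3% | 5.5% / 4.9% | 89.1% / 90.2% |
| 34 | CS, 0.6 | 5.3% | 5.9% / 5.1% | 88.2% / 89.8% |
| 42 | CS, 0.6 | 4.2% | 6.1% / 5.3% | 87.8% / 89.3% |
| 50 | CS, 0.6 | 3.5% | 6.3% / 5.6% | 87.4% / 88.8% |

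In the CS rows REML itself drifts above 5%, so the excess due to ML there is 0.7–0.8 points, not the full distance from 5%.

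**Does Kenward-Roger repair it?** No. Its standard-error adjustment changes the shortfall by under 0.05 percentage points. Its df are larger under ML (about 35 against 31 at N = 34, UN), which slightly lowers the critical value.

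**Second set of correlations.** With 0.7/0.5/0.7 between visits and SD 38.3 at each, the SE ratios are 0.948, 0.958 and 0.965 at n = 34, 42 and 50. On n − 3 df these imply errors of 5.9%, 5.7% and 5.6%, and coverage of 88.2%, 88.5% and 88.8%.

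**The case against.** Nobody would dispute the code or the direction of the bias. The case on the other side is about size and reach.

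- *The primary analysis is larger than 34.* It runs on the FAS with LOCF, so close to 42 or 50 patients contribute; 34 is the completer target and roughly the per-protocol size. This stands. For the primary analysis under UN the relevant range is a 3.1–3.9% shortfall and 5.4–5.8% error.
- *The practical effect is small.* This is a Phase 2a trial of preliminary efficacy. Under the design effect, moving alpha from 5% to 5.5% with 50 patients raises the rejection probability only from 99.3% to 99.4%; moving it to 5.7% with 42 raises it from 98.2% to 98.5%. This also stands. Only a result near the threshold would change.
- *The simulation is idealised.* It uses complete data, one structure at a time and assumed correlations; neither the treatment of LOCF values as observed nor AIC selection was simulated. That limits the precision of the figures. It does not affect the mechanism, which is a known property of ML.
- *The record-position problem is conditional.* It arises only if a missed visit has no row in the dataset. If the row is present with a missing response, order is preserved. The documents do not describe the layout, so this part is a risk rather than a certainty. It concerns the per-protocol analysis, which is the SAP's only sensitivity analysis. Per-protocol patients must have a Week 4 EASI, so any gap falls at Day 8 or Day 15, the pattern that positional matching mishandles.
- *No code is printed for IGA, BSA and PP-NRS.* Carry-over of ML is a fair inference from the instruction to use a similar model, but it is not stated.

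**Conclusion.** The concern holds. The code prescribed for the primary analysis does not deliver the one-sided 5% test or the 90% interval that the SAP promises. Across 34 to 50 patients the standard error is about 3–5% too small (UN 3.1–4.8%, CS 3.5–5.3%). Under UN, as coded, the one-sided error is 5.4–6.0% and coverage 88.0–89.3%. The exact figures depend on visit correlations and a covariance structure that the documents leave open, but every setting examined gave the same direction, and REML was nominal within simulation error under UN.

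Nothing in the plan requires ML. The candidate models differ only in covariance structure and share the same fixed effects, so their AIC values can be compared under REML. This should be corrected, although it is unlikely to change the conclusion if the effect is near the assumed 45 points.

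**What to change.** In the section 12.4.3.4 code, replace `method=ml` with `method=reml`, and write `repeated visit / type=un subject=usubjid;` so that each record is tied to its visit whatever the dataset layout. State REML in the text of that section, and say that it also applies to the IGA, BSA and PP-NRS models. The fixed effects, AIC rule and Kenward-Roger option stay as they are.

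The cost is two code edits and a sentence or two, made before database lock and unblinding. At the FAS size under UN, standard errors rise by about 3–4% (1/(1 − 0.031) = 1.032 to 1/(1 − 0.039) = 1.041), and the reported intervals widen by about the same. At 34 patients the increase is about 5%.

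### The prescribed primary-analysis SAS code sets alpha=0.10 on MODEL only, while the reported treatment differences come from SLICE, so at SLICE's usual 0.05 default they would carry 95% instead of 90% limits

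*SAP*

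**What the plan says.** SAP section 12 sets the testing rule: "Statistical hypothesis testing will be one-sided and carried out at the 5% level of significance". Section 12.4.3.4 applies it to the primary endpoint, with a one-sided p-value compared with 0.05, and adds: "A symmetric two-sided 90% confidence interval will accompany the corresponding p-value". It defines the contrast as ATI-1777 minus vehicle and introduces the program with "The following SAS code will be used".

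Four lines of that program matter here:

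- The procedure call, "proc mixed data= datain method=ml", has no confidence level.
- The MODEL options are "cl solution ddfm=kr alpha=0.10". This is the only place where alpha appears.
- The by-visit treatment comparisons come from "slice treatment * visit /sliceby=visit means diff nob cl", with no alpha.
- The results kept for reporting are "ods output slices = lsm sliceDiffs = diff". Both tables come from SLICE.

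SAP 10.1.3 defines change as the post-baseline value minus baseline, so improvement in EASI is negative. Protocol 9.4.5 describes the one-sided test as one of superiority of ATI-1777 over vehicle.

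**The concern.** The 90% level is attached to output that is not kept (the limits for the fixed-effect solution), and the output that is kept has no level attached. A programmer who runs the code as prescribed would put a 95% interval in a table column that the SAP says holds 90% limits.

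Two things are at stake. The headline interval would be mislabelled. It would also no longer match the test: a two-sided 90% interval excludes zero on the favourable side exactly when the one-sided p-value is below 0.05, and a 95% interval does not have that property. A result could then be reported as significant next to an interval that contains zero.

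The code also stops before the one-sided p-value. No directional option or conversion step is given. The tail has to be chosen with some care, because SAP 8.3 states the planned means as positive numbers (65% and 20%) whereas SAP 10.1.3 makes improvement negative.

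**Working it through.** **Inputs.** From SAP 8.3: 34 evaluable patients, planned means of 65% and 20% (difference 45), a variability figure of 38.3, and stated power of 95.6% for a one-sided contrast in a one-way ANOVA. From SAP 8.4: 1:1 allocation, hence 17 per arm and 32 degrees of freedom. From SAP 12: one-sided alpha of 0.05. SAP 8.3 calls 38.3% a variance; I use it as a standard deviation because that reading reproduces the stated power.

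**The plan's own figure.** The standard error of the difference is 38.3 × √(2/17) = 13.137. The noncentrality is 45 / 13.137 = 3.425. The one-sided 0.05 critical value on 32 df is 1.6939. Noncentral-t power is 95.61%, which matches the stated 95.6%.

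**Interval width.** The half-width is the t quantile times the standard error. This uses the two-sample standard error as an approximation to that of the repeated-measures contrast.

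| Patients | SE | 90% half-width | 95% half-width | Ratio |
|---|---|---|---|---|
| 34 | 13.14 | 1.6939 × 13.137 = 22.25 | 2.0369 × 13.137 = 26.76 | 1.203 |
| 42 (SAP enrolment) | 11.82 | 19.90 | 23.89 | 1.200 |
| 50 (protocol enrolment) | 10.83 | 18.17 | 21.78 | 1.199 |

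The ratio hardly moves with the degrees of freedom, so the Kenward-Roger adjustment would not change it materially. At the planned difference of −45 with 34 patients, the intervals are (−67.3, −22.7) at 90% and (−71.8, −18.2) at 95%.

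**Where the mismatch would show.** With 34 patients, an observed benefit between about 22.3 and 26.8 points gives a one-sided p-value below 0.05 but a 95% interval that contains zero. For example, t = −1.80 corresponds to a difference of −1.80 × 13.137 = −23.65. The specified 90% interval is −23.65 ± 22.25, or (−45.9, −1.4). The 95% interval is −23.65 ± 26.76, or (−50.4, 3.1).

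**The p-value.** For the same t = −1.80 on 32 df, the two-sided p-value is 0.081 and the one-sided p-value in the favourable direction is 0.041. Neither depends on alpha, which sets the confidence level and nothing else. Adding alpha=0.10 to SLICE therefore corrects the interval and leaves the p-value two-sided.

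**Power, if the text were disregarded.** Comparing the two-sided p-value with 0.05 moves the critical value from 1.694 to 2.037. One-sided type I error becomes 0.025 and power at 17 per arm becomes 91.3%.

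**The case against.** The strongest reply is that the SAP text leaves no doubt about what is to be reported. Sections 12 and 12.4.3.4 both call for a one-sided test at 0.05, and 12.4.3.4 also specifies the 90% interval. The code block is plainly not a full reporting program: it ends in output datasets and fits only the unstructured covariance, although the text requires four structures and a choice by AIC. Later steps are expected, and the 90% limits and the one-sided p-value can both be computed from the printed estimate, standard error and degrees of freedom. Unchanged output would err on the conservative side.

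Most of this stands, and it limits the harm. It does not remove the interval error. The SAP says this code will be used, whereas the logistic code in 12.4.4.1 is offered as an example, and no later step to recompute the limits is described.

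Two further points are fair. The SAS default is not stated in the documents. The code listing also has a small irregularity: the severity variable is written with a space in CLASS and an underscore in MODEL, so characters may have been lost in the text. That does not suggest that an option is missing from SLICE, but the source file should be checked.

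A reader might go further and infer that the missing alpha also makes the reported p-values wrong, or that the trial loses power. The documents do not support that. The missing alpha has no bearing on the p-value, and the 91.3% figure applies only if someone compares the two-sided p-value with 0.05, contrary to 12.4.3.4.

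**Conclusion.** The interval error stands: the prescribed code does not deliver the prescribed interval. Assuming SLICE applies its own default of 0.05, the Week 4 difference would carry 95% limits about 20% wider than specified (half-width 26.8 against 22.3 points at 34 patients, taking 38.3 as a standard deviation and using a two-sample standard error). If SLICE instead took its level from MODEL, the limits would be 90% and nothing would be wrong. The code as written relies on that without saying so.

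The one-sided p-value is a secondary matter of completeness. The test is fully fixed by the text; only the step from printed output to reported value is unwritten. The model, the type I error and the planned 95.6% power are unaffected as long as the text is followed.

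**What to change.** In SAP 12.4.3.4, add alpha=0.10 to the SLICE statement. Then add one line stating that the one-sided p-value is the lower-tail probability of the t statistic for ATI-1777 minus vehicle on its Kenward-Roger degrees of freedom, a negative difference being favourable because percent change is post-baseline minus baseline.

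Carry both changes into the code for the continuous secondary endpoints, which use a similar model. Give the logistic example in 12.4.4.1 the same treatment: it too has no alpha and no one-sided step, although 12.4.4 asks for 90% intervals and one-sided p-values.

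The cost is one option and a short data step per program, made before database lock and unblinding. No data collection, model or sample size changes.

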#### 12.4.3.5. Sensitivity Analyses

The population-level summary for the primary estimand based on the FAS population will be repeated using the Per-Protocol population to assess the sensitivity of the analysis to compliance to treatment administration and adherence to protocol specified procedures. Other secondary efficacy analyses and summaries are intended to support the primary estimand and do not qualify as sensitivity analyses.

#### 12.4.4. Secondary Analyses

Treatment comparisons between ATI-1777 and vehicle for each of the continuous efficacy endpoints that are conducted over time (change in IGA, BSA, and PP-NRS) will be analyzed using a similar model as described for the primary endpoint. Treatment comparisons will be made for each post-baseline scheduled visit utilizing the analysis window scheme described in [Section 10.1.1](#). Change from baseline is calculated as described in [section 10.1.3](#).

Treatment group comparisons for categorical efficacy endpoints (IGA response, EASI-50, EASI-75, and EASI-90) that are conducted over time will employ a logistic regression model fit at each scheduled visit separately, where appropriate. The logistic regression model will include treatment group and baseline severity of AD as a factor, and the baseline value as a covariate. Model-based point estimates for the treatment proportions will be provided as well as model-based differences and corresponding symmetric 90% confidence intervals and one-sided p-values. If the Logistic model will not converge or if there is strong collinearity between the baseline EASI score and the baseline severity of AD, one or both of the covariates may be excluded from the secondary analysis.

The secondary efficacy endpoints are

- Percent change from baseline in EASI score at each study visit
- Proportion of patients achieving an IGA score of 0 to 1 combined with an improvement of 2 or more points from baseline within 4 weeks of the start of treatment
- Proportions of patients who achieve EASI-50, EASI-75, and EASI-90 within 4 weeks of the start of treatment
- Change from baseline in IGA score at each study visit
- Change from baseline in BSA at each study visit
- Change from baseline in PP-NRS score over time

##### 12.4.4.1. EASI, EASI-50, EASI-75 and EASI-90

The analysis of percent change from baseline in EASI score at each visit for FAS will be in the same model as the primary efficacy analysis. The estimates at the timepoint other than Week 4 will be considered as secondary endpoints.

EASI-50, EASI-75 and EASI-90 are the proportions of patients achieve 50%, 75%, 90% improvement in EASI score respectively within 4 weeks of the start of the treatment. The follow is an example of EASI-50 definition.

EASI-50 = “YES” If (EASI score at Day 28 – baseline EASI)/baseline EASI  $\geq 50\%$

The follow SAS code is an example for the analysis of EASI-50 at Day 28.

```

proc logistic data= datain;
  class treatment baseline ADseverity;
  model EASI_50 = baseline EASI treatment baseline ADseverity / expb;
  oddsratio treatment;
  lsmeans treatment / e diff oddsratio cl adjust = bon;
run;

```

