3.2 Secondary Endpoints

The secondary endpoints are:

- Percent change from baseline in EASI score at each study visit
- Proportion of patients achieving an IGA score of 0 to 1 combined with an improvement of 2 or more points from baseline within 4 weeks of the start of treatment
- Proportions of patients who achieve 50%, 75%, and 90% improvement in EASI score (EASI-50, EASI-75, and EASI-90, respectively) within 4 weeks of the start of treatment
- Change from baseline in IGA score at each study visit
- Change from baseline in AD BSA at each study visit
- Change from baseline in PP-NRS score over time

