### 8.3. Sample Size Considerations

A total of approximately 42 patients will be enrolled and randomized in order to achieve 34 patients who complete the study. Data from 34 patients provides 95.6% power to detect a statistically significant difference between the treatment groups in the primary endpoint (percent change from baseline in EASI scores). This power calculation is based upon a 1-sided treatment contrast within 1-way ANOVA model and assumes group means of 65% and 20% for ATI-1777 and vehicle, respectively. The group means were based upon slightly more conservative estimates than were observed in a Phase 2 study of topical ruxolitinib in AD. (Kim et al 2020b) The variance for the percent change from baseline in EASI was assumed to be 38.3%. This variance assumption was based upon data observed in a pilot AD study for the topical compound ATI-502 (ATI-502-AD-201).

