### 10.1.3. Change from baseline

Change from baseline (CFB) will be calculated as (post-baseline – baseline). CFB will be calculated for patients with both a baseline and post-baseline value as applicable.

Percent CFB will be calculated as (CFB/baseline)\*100, where applicable.

If a baseline value has not been recorded for a parameter, then CFB will not be calculated for that parameter.

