**Table 4 Extent of Atopic Dermatitis in Each Body Region**

| % Involvement | 0% | 1% to 9% | 10-29% | 30-49% | 50-69% | 70-89% | 90-100% |
|---------------|----|----------|--------|--------|--------|--------|---------|
| Region Score  | 0  | 1        | 2      | 3      | 4      | 5      | 6       |

For each respective body region, the severity of each of 4 signs (erythema, edema/papulation, excoriation, lichenification) will be graded by the investigator or qualified designee on a 0- to 3-point scale ([0] none, [1] mild, [2] moderate, [3] severe) in AD-affected areas. Half scores are allowed. The average severity across AD-affected areas in each body region will be used as the score for that region.

The final EASI score will then be calculated by an electronic data capture system as described in [Table 5](#).

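### SAP 12.4.4.1 writes the EASI-50 rule with the wrong sign: it counts patients whose EASI rose by at least half, and no improved patient can be a responder

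*SAP*

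**What the plan says.** Protocol Section 3.2 lists the responder endpoints as "Proportions of patients who achieve 50%, 75%, and 90% improvement in EASI score". SAP Section 12.4.4.1 repeats this in words: "EASI-50, EASI-75 and EASI-90 are the proportions of patients achieve 50%, 75%, 90% improvement in EASI score respectively". It then gives what it calls an example for EASI-50: the patient is YES when "EASI score at Day 28 – baseline EASI)/baseline EASI" is 50% or more. Neither document gives any other formula for an EASI responder, and EASI-75 and EASI-90 have none.

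Two other parts of the SAP fix the direction of the arithmetic.
- **Sign of change.** Section 10.1.3 states: "Change from baseline (CFB) will be calculated as (post-baseline – baseline", and percent change divides this by baseline.
- **Direction of the scale.** The text under Table 4 grades each sign "on a 0- to 3-point scale ([0] none, [1] mild, [2] moderate, [3] severe", so a higher EASI means worse disease.

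SAP Section 12.4.4 analyses these endpoints by logistic regression at each scheduled visit. If the model fails to converge or the covariates are collinear, "one or both of the covariates may be excluded from the secondary analysis".

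**The concern.** The formula subtracts in the order follow-up minus baseline but keeps a positive cut-off, so it selects worsening. The words and the formula in the same section therefore define opposite groups of patients.

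The formula is the only operational rule that a programmer has for three secondary endpoints. If it is followed as written, nearly everyone becomes a non-responder.
- If both arms have no responders, there is nothing to model.
- If only one arm has none, the logistic treatment coefficient has no finite maximum-likelihood estimate. Dropping covariates, the SAP's stated fallback, does not change that.
- Any responders that did appear would be patients who got worse. They would be expected mainly on vehicle, so the comparison would point the wrong way.

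**Working it through.** **1. The inequality itself.** No assumption is needed here. Let b be baseline EASI and x the Day 28 score. The written rule is (x - b)/b >= 0.50, that is, x >= 1.5b. With b = 20:

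| Day 28 EASI | (x - b)/b | Written rule | Intended rule, (b - x)/b >= 50% |
|---|---|---|---|
| 0 (cleared) | -100% | NO | YES |
| 2 | -90% | NO | YES |
| 5 | -75% | NO | YES |
| 10 | -50% | NO | YES |
| 20 | 0% | NO | NO |
| 29.8 | +49% | NO | NO |
| 30 | +50% | YES | NO |
| 40 | +100% | YES | NO |

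The ratio cannot go below -100% and is below zero for any improvement, so no improved patient can be YES at any baseline.

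**2. Inputs for the size of the effect.** SAP Section 8.3 gives group means of 65% and 20%, read here as improvement; 34 evaluable patients (17 per arm at 1:1); 95.6% power; and "The variance for the percent change from baseline in EASI was assumed to be 38.3"%. The one-sided 5% level is in SAP Section 12.

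Reproducing the plan's own power with 38.3 taken as an SD: noncentrality = 45/(38.3 x sqrt(2/17)) = 3.425 on 32 df, one-sided critical t = 1.694, power = 0.956. This matches the plan. Taken as a true variance, 38.3 gives power of essentially 100%, so the SD reading is used below.

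**3. Expected responder rates.** Assume percent change is normal with mean -65 (ATI-1777) or -20 (vehicle) and SD 38.3. For cut-off c and mean improvement m:
- written rule: P = 1 - Phi((c + m)/38.3)
- intended rule: P = 1 - Phi((c - m)/38.3)

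For EASI-50:
- written: 1 - Phi(115/38.3) = 0.0013 on ATI-1777; 1 - Phi(70/38.3) = 0.0338 on vehicle
- intended: 1 - Phi(-15/38.3) = 0.652 on ATI-1777; 1 - Phi(30/38.3) = 0.217 on vehicle

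The EASI-75 and EASI-90 rows apply the same formula by analogy.

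| Endpoint | Written, ATI-1777 vs vehicle | Intended, ATI-1777 vs vehicle | Expected responders with 25 per arm: written | Intended |
|---|---|---|---|---|
| EASI-50 | 0.13% vs 3.4% | 65.2% vs 21.7% | 0.03 vs 0.84 | 16.3 vs 5.4 |
| EASI-75 | 0.013% vs 0.66% | 39.7% vs 7.5% | 0.003 vs 0.16 | 9.9 vs 1.9 |
| EASI-90 | 0.003% vs 0.20% | 25.7% vs 3.4% | 0.001 vs 0.05 | 6.4 vs 0.8 |

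**4. Chance of empty cells.** For EASI-50 with n per arm, the chance of no responder in either arm is [(1 - 0.00134)(1 - 0.0338)]^n:
- n = 25 (Protocol, 50 patients): 0.409
- n = 21 (SAP, 42 patients): 0.472
- n = 17 (34 evaluable): 0.545

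With 25 per arm, the chances for EASI-75 and EASI-90 are 0.846 and 0.950. The chance that the ATI-1777 arm alone has none is (1 - 0.00134)^25 = 0.967 for EASI-50, and 0.997 and 0.999 for the other two.

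**5. Sensitivity to the SD.** For SD 25 to 50, the written EASI-50 rates run from 0.0% to 1.1% on ATI-1777 and from 0.3% to 8.1% on vehicle. The intended rates are 62% to 73% and 12% to 27%. The direction is reversed throughout. The chance of a wholly empty EASI-50 table depends more on the SD: with 25 per arm it is about (1 - 0.00256)^25 = 0.94 at SD 25 and [(1 - 0.0107)(1 - 0.0808)]^25 = 0.09 at SD 50.

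**6. Limit of the normal model.** It puts 1 - Phi(35/38.3) = 18% of the ATI-1777 arm below -100%, which is impossible. Moving those patients to exactly -100% changes none of the rates, because every cut-off lies above -100%.

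**The case against.** The intent is not in doubt. The endpoint is stated correctly in words wherever it is described, including the sentence directly above the formula, and the formula is offered only as an example. The sample-size text also writes improvement as a positive number, which suggests loose sign shorthand and not a different endpoint. A programmer would probably follow the words. If not, a table with almost no responders beside a large mean fall in EASI would be noticed. The endpoints are secondary, in a Phase 2a trial without multiplicity control. The EASI-75 and EASI-90 figures describe formulas that the SAP does not contain.

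Much of this is fair and limits the weight of the point. This is a sign slip, it is confined to secondary endpoints, it reaches EASI-75 and EASI-90 only by analogy, and it would probably be visible in the output. It does not make the formula right. The formula is the only operational derivation given, and it conflicts with the definition it is meant to illustrate. If the slip were noticed only when the tables looked odd, a responder definition would have to be changed after unblinding, which a pre-specified plan is meant to avoid.

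**Conclusion.** The rule is wrong as written. That conclusion rests only on the printed inequality, the SAP's sign convention and the direction of the EASI scale; it needs no distributional assumption. The size is illustrative: EASI-50 of about 0.1% versus 3.4% in place of about 65% versus 22%, with at least a 97% chance (25 per arm) of no responder on ATI-1777 at each threshold. Those figures assume normal percent change, the planning means, and 38.3 as an SD. The primary endpoint, its one-sided test and the 95.6% power do not use this rule and are unaffected. It should be corrected because the formula gives an invalid result if followed and the repair is trivial.

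**What to change.** Replace the formula in SAP Section 12.4.4.1 and write out all three rules:
- EASI-50 = YES if (baseline EASI - EASI at visit)/baseline EASI >= 50%, equivalently percent change from baseline <= -50%.
- EASI-75 = YES if percent change from baseline <= -75%.
- EASI-90 = YES if percent change from baseline <= -90%.

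The words *at visit* replace *Day 28* so that the rule serves the visit-by-visit models in SAP Section 12.4.4. If the text is to remain a Day 28 example, keeping Day 28 and reversing only the subtraction corrects the sign equally well.

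Made before database lock and unblinding, this is a one-line SAP correction (plus the two added formulas) with no operational cost. The documents do not show whether lock has taken place; if it has, record the correction and its reason as a change to the plan.
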